1.0 BACKGROUND AND HYPOTHESES

Background

Vitamin D is a fat-soluble vitamin that plays an important role in immune modulation in addition to its classical roles in regulation of calcium homeostasis and bone health (1). Vitamin D undergoes two subsequent hydroxylation reactions to form the active metabolite, 1,25(OH)₂D. 25(OH)D, which is an intermediate inactive metabolite, is the major circulating form of vitamin D, and its total serum concentration is used to assess the overall vitamin D status of an individual. Vitamin D insufficiency is defined as a serum 25(OH)D level between 29 and 20 ng/mL, while vitamin D deficiency is defined as a serum 25(OH)D levels below 20 ng/mL. Identification of vitamin D receptors and vitamin D-metabolizing enzymes (CYP27B1, CYP24A1) in immune cells revealed the immune-modulating activity of vitamin D. There is a plethora of evidence of anti-inflammatory effect for vitamin D through inhibition of pro-inflammatory cytokine expressions (2-4).

Current recommended threshold for vitamin D adequacy has been controversial. According to the Endocrine Society, target 25(OH)D level of 30 ng/mL (or 75 nmol/L) is based on the finding that it is the minimal concentration required for optimal bone health while maximally suppressing parathyroid hormone productions in adults (5-7). However, in vitro study revealed that concentrations greater than 30 ng/mL may be required to have maximal anti-inflammatory effect (8). Clinical consequences of vitamin D inadequacy go well beyond osteoporosis; vitamin D deficiency is associated with increased risks of several diseases, including diabetes, cancer and inflammatory diseases (9-13). Accordingly, several studies demonstrated a positive effect of vitamin D supplementation on inflammatory markers indicating that correcting vitamin D status may serve as an effective anti-inflammatory therapy (14-16).

Cystic Fibrosis and Vitamin D deficiency

Cystic fibrosis (CF) is a lethal autosomal recessive disorder characterized by chronic airway infections, inflammation and obstruction, leading to progressive loss of lung function and ultimately respiratory failure. Vitamin D deficiency is highly prevalent in CF patients, affecting approximately 90% of patients with CF (17, 18). Malabsorption of fat-soluble vitamins, which is a result of exocrine pancreatic enzyme insufficiency, likely play a role in vitamin D deficiency (19). Over 85% of CF patients are affected by pancreatic insufficiency, which causes intestinal malabsorption of nutrients, such as vitamin D (20). In addition to malabsorption, other factors may also contribute to suboptimal vitamin D status, including reduced exposure to sunlight, reduced levels of vitamin D binding proteins and poor adherence to daily dosing (20-22). Inadequate vitamin D level is of particular concern for patients with CF as vitamin D deficiency has been associated with increased risk of respiratory infection and worsened pulmonary function (21).

Study Rationale

Despite the extensive literatures on adverse clinical outcomes associated with vitamin D deficiency and beneficial effects of vitamin D supplementation in the treatment of various inflammatory and infectious diseases, there are currently no proven treatment strategy that effectively achieves and maintains optimal serum vitamin D status in CF patients (23). For the treatment of vitamin D deficiency in CF, CF Foundation currently recommends 2,000 IU daily (24). However, because achieving adequate serum 25(OH)D levels is a challenge in CF, higher doses of vitamin D may be necessary to reach and maintain vitamin D sufficiency (25, 26). A pilot study of vitamin D supplementation in adults with CF experiencing pulmonary exacerbation revealed that high dose of vitamin D (250,000 IU) raised 25(OH)D levels while it did not cause hypercalcemia or significant changes in PTH concentrations (26), which indicates that this mega-dose of vitamin D3 is safe in CF patients. In addition, several studies in non-CF population have demonstrated that high single doses of vitamin D3 did not significantly alter the PTH or calcium levels (27-29). In a retrospective chart

review of pediatric CF patients, majority of patients (79%) rapidly and safely achieved and sustained optimal 25OHD levels over a 12 month period with a single high-dose oral vitamin D3 (300,000 IU – 600,000 IU), also known as stoss therapy (25). However, approximately 20% of patients still could not achieve levels above 30 ng/mL. Wide inter-individual variability in response to vitamin D treatment has been previously reported in non-CF population, suggesting that fixed-dose approach to replacement therapy may not be effective in improving 25(OH)D status in CF (30). Poor oral bioavailability of ergocalciferol has been demonstrated in CF patients (31), which suggests that CF patients may potentially exhibit low absorption of cholecalciferol. Therefore, based on the degree of malabsorption of vitamin D and basal vitamin D status, supplementation should be tailored to individuals. In order to optimize the treatment of deficiency in CF, kinetic disposition of vitamin D must be well understood. However, there are very few data currently available describing the kinetics of both vitamin D and 25-hydroxyvitamin D, and to the investigator's knowledge, no studies have yet characterized the pharmacokinetic disposition of vitamin D in cystic fibrosis. Addressing this issue is crucial in effectively and safely correcting vitamin D deficiency in CF.

Our study hypothesis is that CF patients with vitamin D deficiency exhibit altered pharmacokinetics of vitamin D and 25(OH)D when compared to non-CF subjects with vitamin D insufficiency or deficiency.

2.0 OBJECTIVES AND PURPOSE

2.1 Primary Objective:

Characterize the pharmacokinetics of vitamin D3 and 25(OH)D3 with a single, high-dose of vitamin D3 in adults with CF.

Compare the pharmacokinetics of vitamin D3 and its metabolites between non-cystic fibrosis controls with low vitamin D levels and adults with cystic fibrosis

2.2 Secondary Objective:

Assess the anti-inflammatory effects of high dose vitamin D therapy in adults with CF.

3.0 STUDY DESIGN

This is a pilot study to determine the pharmacokinetics-pharmacodynamics of vitamin D3 in CF patients. Clinically stable CF patients with a history of pancreatic insufficiency (n=6) and matching non-CF subjects (n=6) will be recruited in this study. The presence of pancreatic insufficiency will be based on a known CF genotype associated with pancreatic insufficiency. All subjects will be pre-screened for 25(OH)D status to include those with 25(OH)D levels below 30 ng/mL. The subjects will receive a single oral dose of vitamin D3, known as stoss therapy. The dose of stoss therapy will be based on patient's baseline serum 25-hydroxyvitamin D3 level. For CF patients, the dose will be administered with food and pancreatic enzyme supplement to maintain nutritional status. This dose was chosen because previous studies in pediatric CF patients demonstrated that a large single dose of up to 600,000 IU vitamin D3 raised and maintained sufficient 25(OH)D concentrations over 12 weeks without any signs of adverse events (25, 26).

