6.0 STRATIFICATION/DESCRIPTIVE FACTORS/RANDOMIZATION SCHEME

6.1 Stratification factors: Not applicable

6.2 Descriptive factors. Not applicable

7.0 STUDY AGENT ADMINISTRATION OR INTERVENTION AND TOXICITY MANAGEMENT PLAN

7.1 Patients will be given a single dose, oral capsule of vitamin D3 based on measured 25-(OH) vitamin D level (25).

7.2 Drug studies:

AGENT	DOSE	ROUTE	DAYS	ReRx	NOTES
Cholecalciferol	600,000 IU	PO	1	Once	25-(OH) vitamin D \leq 25 nmol/L (\leq 10 ng/mL)
Cholecalciferol	500,000 IU	PO	1	Once	25-(OH) vitamin D 25-50 nmol/L (10-20 ng/mL)
Cholecalciferol	300,000 IU	PO	1	Once	25-(OH) vitamin D 50-75 nmol/L (20-30 ng/mL)

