13.0 STATISTICAL CONSIDERATIONS

13.1 Pharmacokinetic Analysis

Population pharmacokinetic analysis will be performed using the maximum likelihood estimation via the EM algorithm (MLEM) as implemented in ADAPT 5 (Biomedical Simulations Resource, University of Southern California). Multiple candidate models will be evaluated to identify the model that best describes the observed plasma concentration data for vitamin D3 and 25(OH)D3. The maximum concentration and time to maximum concentration will be determined from the observed data.

Patient demographics, clinical characteristics, and pharmacokinetic parameters will be summarized using descriptive statistics.

Differences in the pharmacokinetic parameters between non-CF controls and CF patients will be determined by non-parametric Wilcoxon-Mann Whitney test.

13.2 Comparison of mean serum and plasma concentrations of inflammatory markers at baseline and 10 weeks post intervention

Mean serum/plasma concentrations of inflammatory biomarkers will be compared between CF and non-CF, as well as within groups. Differences in the mean concentrations of inflammatory markers will be determined by non-parametric Wilcoxon-Mann Whitney test.

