Appendix I: Study Calendar

Appendix I

	Screening	Day 0	Day 1	Day 7	Day 28	Day 56	Day 70
Informed Consent	X						
Medical History	X						
Medication History	X						
Height, weight	X						
Vital signs ^A	X	X	X	X	X	X	X
Safety labs ^B	X			X			
Pre-screening of 25OHD status	X						
PO drug administration		X					
Blood Pharmacokinetics (PK) ^C		X	X	X	X	X	X
Blood inflammatory biomarkers		X	X	X	X	X	X
Adverse Events		X	X	X	X	X	X

A. Vital signs to include blood pressure, heart rate, temperature, respiratory rate.

B. Safety labs to include comprehensive metabolic panel

C. All subjects will have a pre dose blood PK levels, 2, 4, 6, 8 hours and 1, 7, 28, 56, 70 days post dose of cholecalciferol. A 5mL serum separator tube will be used to collect the blood sample.

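### Food at dosing is specified for CF patients only and no meal condition is set for controls, so meal state can differ by group in the primary CF versus non-CF pharmacokinetic comparison

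*Combined protocol and SAP*

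**What the plan says.** Section 2.1 lists two primary objectives. The first describes pharmacokinetics in CF adults. The second is to "Compare the pharmacokinetics of vitamin D3 and its metabolites between non-cystic fibrosis controls with low vitamin D levels and adults with cystic fibrosis". Section 10.0 makes Cmax, Tmax and AUC the primary outcomes, and Section 11.0 samples at 0, 2, 4, 6 and 8 hours and then from day 1 to day 70.

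On dosing, Section 3.0 says of everyone: "The subjects will receive a single oral dose of vitamin D3, known as stoss therapy". It then adds for one group: "For CF patients, the dose will be administered with food and pancreatic enzyme supplement to maintain nutritional status". Section 7.1 says: "Patients will be given a single dose, oral capsule of vitamin D3 based on measured 25-(OH) vitamin D level". It sets no meal condition. Neither the drug information (Section 4.1), the ancillary treatment rule (7.4), the sampling instructions (11.0) nor the study calendar (Appendix I) sets one for controls. The content of the CF patients' meal is not defined either.

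On analysis, Section 13.1 says: "The maximum concentration and time to maximum concentration will be determined from the observed data". It continues: "Differences in the pharmacokinetic parameters between non-CF controls and CF patients will be determined by non-parametric Wilcoxon-Mann Whitney test". No adjustment is described for that test.

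**The concern.** The question behind the study is largely one of absorption. Section 1.0 attributes vitamin D deficiency in CF partly to malabsorption of fat-soluble vitamins and raises the possibility that cholecalciferol is poorly absorbed in CF. A meal given with the dose in one group and left open in the other may act on the very process being compared.

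If food raises absorption and CF patients are fed more often than controls, the CF/control ratio for Cmax and AUC is biased upward. A true CF deficit becomes harder to see. With no true difference, or a small one, the same bias can produce a spurious finding of higher exposure in CF. Both errors count, because the hypothesis in Section 1.0 is only that CF patients "exhibit altered pharmacokinetics of vitamin D and 25(OH)D when compared to non-CF subjects", with no direction given.

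In the extreme case, where every CF patient is fed and no control is, meal and disease coincide completely. No covariate, whether in the population model or in an adjusted test, could then separate them. That is why this belongs in the dosing instructions and cannot be left to the analysis.

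**Working it through.** The plan gives no power, alpha, CV, target ratio or meal effect, so there is no stated figure to reproduce. The calculation below is an illustration only.

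**From the documents.** 6 CF and 6 non-CF subjects (Section 3.0); Wilcoxon-Mann-Whitney test (13.1); food specified for CF only (3.0).

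**Assumed.** Two-sided test at 0.05; log-normal vitamin D3 Cmax or AUC; between-subject CV 40% (also 60%); equal dose in both groups; food multiplies exposure by 1.3 (range 1.2 to 1.5); every CF patient fed; true CF/control ratio 0.50 or 1.0.

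**Step 1: rejection region.** With 6 versus 6 there are C(12,6) = 924 equally likely rank arrangements under no difference. Rejecting when U ≤ 5 or U ≥ 31 takes in 19 arrangements at each end, so the exact size is 38/924 = 0.0411.

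**Step 2: size of the bias.** On the log scale, σ = √ln(1 + CV²). This is √ln(1.16) = 0.385 at CV 40% and √ln(1.36) = 0.555 at CV 60%. If no control is fed, the ratio the trial estimates is the true ratio times the meal effect: 0.50 × 1.3 = 0.65, or 1.0 × 1.3 = 1.3.

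**Step 3: rejection rates.** 200,000 simulated trials per cell, 1.3-fold meal effect. In the middle rows each control is fed independently with the stated chance.

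| Feeding of controls | CV 40%: power at ratio 0.50 | CV 40%: false rejection at 1.0 | CV 60%: false rejection at 1.0 |
|---|---|---|---|
| All fed, as in CF | 74% | 4% | 4% |
| 80% chance each | 66% | 4% (4.4%) | – |
| 50% chance each | 54% | 7% | 5% |
| None fed | 36% | 16% | 10% |

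At CV 40% with no control fed, almost all of the 16% are results in the direction of higher exposure in CF (15.6 of 15.7 percentage points). At CV 60%, power at ratio 0.50 starts at 44% and falls to 19% with no control fed.

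**Step 4: sensitivity to the meal effect.** With no control fed and CV 40%, a meal effect of 1.2 gives power 48% and false rejection 10%. A meal effect of 1.5 gives 18% and 33%.

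**Step 5: sensitivity to dose.** Section 7.2 gives 300,000, 500,000 or 600,000 IU according to baseline 25(OH)D. With one third of subjects in each tier in both groups (assumed) and no dose normalisation, the CV 40%, 1.3-fold case with no control fed moves power from 54% to 24% and false rejection from 4% to 11%.

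**Step 6: total 25(OH)D3.** A pre-dose level dilutes the effect if it is not subtracted. With baseline 20 ng/mL and a rise of 30 ng/mL (both assumed), a 1.3-fold effect on the rise changes Cmax by (20 + 30 × 0.5 × 1.3)/(20 + 30 × 0.5) = 39.5/35 = 1.13 when the true rise ratio is 0.50. When it is 1.0 the factor is (20 + 30 × 1.3)/(20 + 30) = 59/50 = 1.18. In simulation (baseline SD 5, CV of the rise 40%) power falls from 58% to 28% and false rejection rises from 4% to 14%, again with no control fed.

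Tmax was not modelled, and no direction is claimed for it.

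**The case against.** A reader might infer that controls will be dosed fasting, or that the plan sets up a fed-versus-fasted contrast. The documents do not support this. They are silent on controls. The food sentence pairs food with enzymes and gives a nutritional reason, so it reads as an instruction for CF care.

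It is tempting to argue that the plan names both groups whenever it means both, as in Appendix I: "All subjects will have a pre dose blood PK levels". But the drafting is not that consistent. Section 8.11 introduces the safety laboratory tests as protection for CF patients, while the calendar lists them without a group limit. Section 7.1 speaks of patients where Section 3.0 doses all subjects. The wording alone does not show that controls are to be handled differently. Consent material was not among the documents reviewed, and eating instructions there cannot be ruled out.

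It is also fair to say that the largest figures assume no control is fed. Silence may more naturally lead to a mixture, and with an 80% chance of feeding per control the false rejection rate is barely above nominal. The existence, size and direction of a food effect are assumed. This is a pilot of 12 subjects with no stated power, so loss of power contradicts no claim in the plan.

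These objections reduce the size of the point but do not remove it. Section 3.0 calls the controls matching but names no matching factors, so matching does not settle meal state. The comparison is a primary objective whatever the sample size. Enzymes will remain a CF-only difference after any fix, but they belong to CF treatment; the meal need not differ.

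**Conclusion.** The point holds as a gap in the dosing instructions: food is specified for one group and left open for the other, in a primary comparison of outcomes that depend on absorption. The documents do not show that meal state will differ, only that the plan allows it. If controls are fed in the same way as CF patients, the problem disappears.

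The size depends on three things the documents do not give: the meal effect, the CV and how many controls eat. For a given meal effect and CV, the figures with no control fed are an upper bound and should not be read as the expected loss. The inflation of false rejection is smaller at CV 60%, and both effects are somewhat smaller for total 25(OH)D3 than for vitamin D3. The upward direction for Cmax and AUC rests on food raising absorption. The first primary objective, describing pharmacokinetics in CF adults, is not affected by this imbalance.

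The change is worth making before dosing starts, because complete confounding cannot be undone afterwards. Confidence is medium, since the practice intended for controls is unknown.

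**What to change.** In Sections 3.0 and 7, state that both groups take the dose with the same defined meal, and that pancreatic enzymes in CF are the only intended difference in administration. Record the meal and the dosing time for every subject on Day 0, with a matching line in the Appendix I calendar.

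The cost is one or two sentences of protocol text, one entry on the case report form, and the same meal for six controls.

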4.0 DRUG/DEVICE INFORMATION

4.1 Vitamin D3 (Cholecalciferol)

Currently, best approach to treat vitamin D deficiency is vitamin D supplementation. Cholecalciferol has shown to be effective in raising serum 25(OH)D concentrations in adult CF patients (32). Each patient will be given vitamin D3 50,000 IU capsules from BioTech Pharmacal Inc. Vitamin D3 is considered a dietary supplement and therefore is not part of FDA-regulated drugs.

5.0 SELECTION AND WITHDRAWAL OF SUBJECTS

5.1 Inclusion Criteria (CF) :

Diagnosis of CF based on positive sweat chloride or known CF mutation
Patients with pancreatic insufficiency
Age \geq 18 years
Serum 25(OH)D concentrations below 30 ng/mL (75 nmol/L)

Inclusion Criteria (non-CF) :

Age \geq 18 years
Serum 25(OH)D concentrations below 30 ng/mL (75 nmol/L)

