5.2 Exclusion Criteria

Pregnancy
History of lung transplant,
Severe anemia (hemoglobin concentration $<$ 7 g/dL),
Liver disease (AST/ALT $>$ 3x ULN), kidney disease (GFR \leq 40 mL/min), or
granulomatous conditions
Patients taking steroids, cholesterol-lowering drug (cholestyramine), weight-loss
drugs (Orlistat) , statins, anti-tuberculosis drugs (rifampin and isoniazid),
phenobarbital, phenytoin, carbamazepine, immunosuppressant (cyclosporine,
tacrolimus) (33, 34)

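### Non-CF controls are selected for low 25(OH)D, and fat-malabsorbing disease or surgery is not excluded, so a control can share the mechanism proposed for CF

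*Combined protocol and SAP*

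**What the plan says.** **Design.** Section 3.0: "Clinically stable CF patients with a history of pancreatic insufficiency (n=6) and matching non-CF subjects (n=6) will be recruited in this study". No matching variable is named there or elsewhere, and clinical stability is asked only of the CF patients. Both groups are selected on low vitamin D: "All subjects will be pre-screened for 25(OH)D status to include those with 25(OH)D levels below 30 ng/mL".

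**Control eligibility.** In Section 5.1, the list that begins "Inclusion Criteria (non-CF" has two items: age 18 or over, and 25(OH)D below 30 ng/mL.

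**Exclusions.** Section 5.2 is not split by group, so I read it as applying to both. Its disease items are pregnancy, lung transplant, severe anemia, liver disease, kidney disease and "granulomatous conditions". Its drug item opens "Patients taking steroids, cholesterol-lowering drug (cholestyramine), weight-loss" and goes on to orlistat, statins, anti-tuberculosis drugs, anticonvulsants, cyclosporine and tacrolimus. No malabsorptive disease and no gastrointestinal surgery appears.

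**Mechanism and hypothesis.** Section 1.0, on CF: "Malabsorption of fat-soluble vitamins, which is a result of exocrine pancreatic enzyme insufficiency, likely play a role in vitamin D deficiency". The hypothesis closing Section 1.0 concerns people with CF who have low vitamin D, and expects them to "exhibit altered pharmacokinetics of vitamin D and 25(OH)D when compared to non-CF subjects with vitamin D insufficiency or deficiency". Section 2.1 makes the CF versus non-CF comparison a primary objective, Section 10.0 lists Cmax, Tmax and AUC as primary outcomes, and Section 13.1 tests the group difference with a Wilcoxon-Mann-Whitney test.

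**Screening.** Appendix I schedules a medical and a medication history at screening. No malabsorption criterion acts on the medical history.

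**The concern.** The comparison is meant to show what CF does to the handling of a large oral dose of vitamin D3, and poor absorption is a leading suspected reason for a difference. The comparator should therefore absorb fat normally. The plan already acts on this idea for drugs, since it removes users of cholestyramine and orlistat, but it leaves out diseases and operations with the same effect.

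Selecting controls on low 25(OH)D makes the gap more relevant. Malabsorption lowers 25(OH)D, so people who malabsorb can be over-represented among adults below 30 ng/mL. The documents support the direction of this enrichment but give no rate.

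With six controls, each one is a sixth of the comparator. A malabsorbing control pulls control Cmax and AUC toward the CF values. A null result could then mean that CF does not alter the kinetics, or that some controls shared the defect, and the data as planned would not tell these apart.

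**Working it through.** The plan states no alpha, power, effect size or variance, so it has no figure to reproduce. What follows is an illustration.

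**Inputs from the documents:** 6 CF and 6 non-CF subjects (Section 3.0); Wilcoxon-Mann-Whitney test (Section 13.1).

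**Assumed, not in the documents:** two-sided 0.05; log-normal exposure; CF exposure half of control (ratio r = 0.5); between-subject CV 40%; an affected control drawn from the CF distribution; prevalence p of affected people among eligible controls.

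**1. Rejection region.** There are C(12,6) = 924 equally likely rank allocations under the null. U ≤ 5 covers 19 of them, so rejecting at U ≤ 5 or U ≥ 31 has exact size 2 × 19/924 = 0.041. Extending to U ≤ 6 gives 0.065, which is too large.

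**2. Effect on the log scale.** SD = √ln(1 + 0.4²) = 0.385. Shift = ln 2 = 0.693, or 0.693/0.385 = 1.80 SD.

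**3. Bias in the estimate.** With k affected controls of six, the expected-mean ratio is r / [(6 − k + k·r)/6].
- k = 0: 0.50
- k = 1: 0.5/(5.5/6) = 0.55
- k = 2: 0.5/(5/6) = 0.60

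**4. Chance of detection, given k** (simulated; the last digit can move by about one point between runs):

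| Assumption | k = 0 | k = 1 | k = 2 |
|---|---|---|---|
| r = 0.5, CV 40% | 74% | 48% | 26% |
| r = 0.5, CV 30% | 93% | 65% | 34% |
| r = 0.5, CV 50% | 57% | 35% | 20% |
| r = 0.3, CV 40% | 99% | 79% | 40% |
| r = 0.7, CV 40% | 26% | 18% | 12% |

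**5. Averaging over k.** The number of affected controls is taken as binomial(6, p), so P(at least one) = 1 − (1 − p)⁶. Averaged power is the sum over k of P(k) × power(k). For p = 5% in the base case: 0.735 × 0.744 + 0.232 × 0.477 + 0.031 × 0.260 + 0.002 × 0.136 = 0.67.

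| Assumed p | P(at least one) | P(two or more) | Averaged power |
|---|---|---|---|
| 2% | 11% | 0.6% | 71% |
| 5% | 26% | 3% | 67% |
| 10% | 47% | 11% | 59% |
| 20% | 74% | 34% | 46% |

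Against 74% with no affected control, the expected loss is about 3, 8, 15 and 28 percentage points.

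**The case against.** **The loss depends on an event the documents do not quantify.** The falls to 48% and 26% require that one or two malabsorbing controls actually enroll. At a prevalence of 2% the averaged loss is about 3 points. This stands, and the conditional figures should not be read as the expected result.

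**Affected controls may not behave like CF patients.** Section 3.0 has CF patients take the dose with food and pancreatic enzymes, so their exposure reflects treated insufficiency. An untreated control might have higher or lower exposure than that. Tmax was not modelled. This limits the size. It does not change the direction for an absorption-driven difference in Cmax and AUC, because a malabsorbing control still lowers the control values.

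**This is a pilot with no power claim.** That is so, and if the true ratio were 0.7 the test would have only about 26% power even with six unaffected controls. The first primary objective, describing kinetics in CF, is also untouched by who the controls are. But the group comparison is itself a primary objective with a planned test, and the bias affects the estimate as well as the power.

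**The controls are described as matching, and a history is taken.** Neither closes the gap: no matching variable is stated, and no malabsorption criterion uses the history.

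**Stronger readings that a reader might infer, and that the documents do not support:**
- That a person with Crohn's disease is plainly eligible as a control. The exclusion of "granulomatous conditions" is undefined and may be read to cover Crohn's disease. The other examples do not depend on it.
- That inflammatory disease goes unchecked, so the biomarker comparison is compromised in the same way. Section 1.0 does say "vitamin D deficiency is associated with increased risks of several diseases, including diabetes, cancer and inflammatory diseases", and Section 13.2 compares markers between groups. But the exclusions for granulomatous conditions, steroids, cyclosporine and tacrolimus remove some of that disease, and no size can be put on what is left.
- That choosing controls with low vitamin D is an error. It is deliberate and written into the hypothesis.

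**Conclusion.** The point holds for malabsorption. As written, the plan admits non-CF adults with a disease or operation that impairs fat absorption, selects on a marker that can favour them, and has no other provision that keeps them out. Any such control would bias the Cmax and AUC comparison toward no difference.

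The harm is possible, not certain. Under the base assumptions one affected control moves the expected CF/control ratio from 0.50 to 0.55, and two move it to 0.60. The averaged loss of power is small at a prevalence of 2% and becomes material at 10% or more. The effect size, CV, significance level, prevalence and CF-like behaviour of affected controls are all assumptions. The gap in eligibility is not.

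Residual inflammatory disease in controls is a secondary matter for the biomarker comparison and not part of this conclusion. The change is worth making because it alters who is enrolled at almost no cost.

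**What to change.** Add to Section 5.2, for non-CF subjects only: *known malabsorptive condition or gastrointestinal surgery affecting absorption (e.g. celiac disease, inflammatory bowel disease, bowel resection, bariatric surgery, pancreatic insufficiency of any cause)*. It must be limited to non-CF subjects because Section 5.1 requires pancreatic insufficiency in the CF group. Naming inflammatory bowel disease also settles the doubt over how far the granulomatous item reaches.

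Ascertain it from the medical history already scheduled at screening in Appendix I; no new test or visit is needed. The line covers known conditions only, so undiagnosed malabsorption could still enter.

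The cost is one line of text and a slightly smaller control pool, which should matter little when six controls are needed. A further exclusion for inflammatory disease would need its own definition and is not needed for this change.
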